9.1.4 Lost to Follow-up

A subject will be considered lost to follow-up if both of the following occur:

- The subject misses 2 consecutive study visits (telephone contact and/or clinic visit) and is subsequently unable to be contacted by telephone (3 documented attempts by telephone within 2 weeks following the second missed visit)
- The subject does not respond within 2 weeks to a registered letter sent after the 3 attempted telephone contacts.

9.1.5 Completion of Study Participation

Completion of study participation for each individual subject is defined as: the Safety Follow-up Visit; or, in situations in which the ETT Visit or the Week 96 Visit replace the Safety Follow-up Visit (Section 9.1.2), the ETT Visit or the Week 96 Visit.

If subjects withdraw consent or assent, completion of study participation is defined as date of withdrawal of consent or assent, whichever is earlier (Section 9.9).

If subjects are lost to follow-up (Section 9.1.4), the date of completion of study participation will be defined as the date of last contact.

The end of study is defined in Section 13.2.8.

9.1.6 Independent Data Monitoring Committee

This study will be monitored by an independent data monitoring committee (IDMC), which will conduct periodic reviews of safety data (Section 12.3.6.2). Procedural details of the IDMC structure and function, frequency of meetings, and data planned for review will be included in the IDMC charter. The IDMC charter will be finalized before the first subject is enrolled.

9.2 Method of Assigning Subjects to Treatment Groups

This is an open-label study. Randomization is not required because all subjects will be treated identically in a single cohort.

9.3 Rationale for Study Design and Study Drug Regimens

9.3.1 Study Design

This Phase 3 study will enroll subjects who completed the last Treatment Period visit in a parent study of TC VX-659/TEZ/IVA and meet eligibility criteria. Results from this study will provide information on the long-term safety and efficacy of TC treatment with VX-659/TEZ/IVA in subjects with CF who are aged 12 years and older and homozygous or heterozygous for the *F508del* mutation, as per the populations enrolled in the parent studies.

9.3.2 Study Drug Dose and Duration

All subjects will receive a TC of VX-659/TEZ/IVA at the same dosage as that in the parent studies (including, but not limited to, Study 659-102 and Study 659-103).

The overall treatment duration will be 96 weeks. This duration was employed in open-label extension studies for previously approved CFTR modulators, Kalydeco and Orkambi, and is considered sufficient for the evaluation of long-term safety and efficacy.

9.3.3 Rationale for Study Assessments

All safety assessments are standard parameters for clinical studies in drug development. The PD and efficacy parameters being evaluated (e.g., SwCl, spirometry, PEx, anthropometric measurements, and patient-reported outcomes) are widely accepted and generally recognized as reliable, accurate, and relevant to the study of patients in CF. These parameters were routinely measured in the parent studies, as well as the registration studies of IVA (Kalydeco) or LUM/IVA combination therapy (Orkambi).

9.4 Study Restrictions

9.4.1 Prohibited Medications

[Table 9-1](#) lists prohibited medications. A non-exhaustive list of study prohibitions and cautions for medication will be provided in the Study Reference Manual.

Table 9-1 Prohibited Medications

Medication	Timing of Restriction		Rationale
	Start of Restriction	End of Restriction	
Moderate and strong CYP3A or CYP2C9 inducers	None allowed within 14 days before the first dose of the study drug on Day 1	None allowed through completion of study participation	VX-659, TEZ, and IVA are metabolized extensively via CYP3A4. VX-659 is also metabolized by CYP2C9. Therefore, use of moderate and strong inducers of CYP3A or CYP2C9 and moderate and strong inhibitors of CYP3A, which have the potential to alter the exposure of VX-659, TEZ, or IVA, will be prohibited.
Moderate and strong CYP3A inhibitors (except ciprofloxacin) ^a	None allowed within 14 days before the first dose of the study drug on Day 1	None allowed through completion of study participation	
Sensitive OATP1B1 substrates	None allowed within 14 days before the first dose of the study drug on Day 1	None allowed through completion of study participation	VX-659 is a potential inhibitor of the hepatic transporter OATP1B1. Therefore, sensitive substrates of OATP1B1, such as HMG-CoA reductase inhibitors (“statins”) are prohibited during treatment.
CFTR modulators (investigational or approved), except for study drug in the parent studies and this study	None allowed within 14 days before the first dose of the study drug on Day 1	None allowed through completion of study participation	These agents may confound the results of this study.

CYP: cytochrome P450; IVA: ivacaftor; OATP1B1: organic anion transporting polypeptide 1B1; TEZ: tezacaftor

^a Ciprofloxacin is not a moderate CYP3A inhibitor on the basis of results of a drug-drug interaction study conducted with IVA, a sensitive CYP3A substrate (Kalydeco [ivacaftor] US Package Insert).

9.4.2 Exposure to Sunlight

Subjects will take appropriate measures to minimize exposure to UV radiation (e.g., prolonged sunlight, tanning booths) from Day 1 through completion of study participation.

9.5 Prior and Concomitant Medications

Information regarding prior and concomitant medications, including CF medications, other medications, and herbal and naturopathic remedies, will be collected in each subject’s source documentation for medications taken within the 56 days before the first dose of study drug in this study through completion of study participation, as defined in Section 9.1.5.

- Subjects should remain on a stable treatment regimen for their CF through completion of study participation. Stable treatment regimen is defined as the current treatment regimen for CF that subjects have been following for at least 28 days before Day 1. Subjects should not initiate long-term treatment with new medication from 28 days before the Day 1 Visit through completion of study participation. Subjects who are taking inhaled tobramycin or other chronically inhaled antibiotics should remain on that regimen throughout the study.
- Subjects may receive doses of prednisone or prednisolone of up to 10 mg/day chronically, or up to 60 mg daily for up to 5 days.

- Information about bronchodilator use during the study will be collected and documented. Subjects who are using a bronchodilator must have their spirometry assessments performed according to the guidelines provided in Section 11.6.1.

9.6 Administration

9.6.1 Dosing

Study drug will be administered orally. Additional information is provided in the Pharmacy Manual.

Study drug will be administered with a fat-containing meal or snack, such as a standard “CF” meal or snack or a standard meal.

1. It is recommended that the dose be taken within 30 minutes of the start of the meal or snack.
2. Study drug will be administered as 2 fixed-dose combination (FDC) TC tablets in the morning and as 1 IVA tablet in the evening. For each subject, doses of study drug will be taken at approximately the same time (± 2 hours) each day.
3. The date, amount taken, and time of study drug administration, including whether food was taken with each dose, will be recorded for the 2 doses before pharmacokinetic (PK) sample collection (Week 4) and the dose received on the morning of PK sample collection (Week 4).
4. On days of scheduled visits, the morning dose of TC will be administered at the site after predose assessments have been completed. A meal or snack will be provided by the site for the morning dose of TC.
5. If a subject’s scheduled visit is to occur in the afternoon, the following guidelines must be used:
 - If the dose in the clinic will be within 6 hours of the subject’s scheduled morning dose, the subject should withhold their morning dose of TC and the morning dose of TC will be administered in the clinic.
 - If the dose in the clinic will be more than 6 hours after the subject’s scheduled morning dose of TC, the subject should take the morning dose of TC at home.
6. Subjects will be instructed to bring all used and unused materials associated with the study drug to the site; study drug will be dispensed at each visit, as appropriate.

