3 SCHEDULE OF ASSESSMENTS

[Table 3-1](#) provides the schedule of assessments during the study. All visits will be scheduled relative to the Day 1 Visit in this study.

The Cystic Fibrosis Questionnaire–Revised (CFQ-R) must be completed before any other assessment at relevant clinic visits. Remaining assessments may be performed in any order when more than 1 assessment is required at a particular time point. All assessments will be performed before study drug dosing (Section [9.6.1](#)), unless noted otherwise.

Table 3-1 VX17-659-105: Treatment Period and Safety Follow-up Visit

Event/Assessment ^a	Treatment Period							ETT Visit ^c	Safety Follow-up Visit (28 ± 7 Days After Last Dose) ^d
	Day 1 ^b	Day 15 (± 3 Days)	Weeks 4, 8, 16, 24, 36 (± 5 Days)	Weeks 12, 20, 28, 32, 40, 44, 52, 56, 64, 68, 76, 80, 88, 92 (± 5 Days)	Week 48 (± 5 Days)	Weeks 60, 72, 84 (± 5 Days)	Week 96 (± 5 Days)		
Clinic visit	X	X	X		X	X	X	X	X
Telephone contact				X ^k					
ICF and assent (when applicable)	X ^e								
Inclusion and exclusion criteria confirmation	X								
CFQ-R ^f	X		Weeks 4, 8, 24		X	Week 72	X	X	X
Weight and height ^g	X		X		X	X	X	X	X
Ophthalmologic examination ^h					X		X ⁱ	X ⁱ	X ⁱ

^a All assessments will be performed before dosing unless noted otherwise.

^b The Day 1 Visit of this study will be on the same day as the last scheduled visit of the parent study. Subjects will NOT have to repeat any Day 1 assessments that were specified to be performed at the last scheduled visit in the parent study. Subjects who were enrolled and remained clinically stable but had Day 1 study drug administration procedures delayed by no more than 7 days for reasons not related to their clinical status will have to repeat the safety (Section 11.7) and spirometry (Section 11.6.1) assessments that were specified to be performed at the Day 1 Visit before receiving their first dose of study drug. Subjects who have not received the first dose of study drug within 7 days of the last dose of study drug in the parent study, or subjects who had Day 1 study drug administration procedures delayed by no more than 7 days for a reason related to clinical status, will have to repeat all Day 1 assessments (Section 9.1.1).

^c If the subject prematurely discontinues study drug treatment, an ETT Visit should be scheduled as soon as possible after the decision to discontinue treatment (Section 9.1.3).

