^j Subjects will have a complete physical examination as defined in Section 11.7.3. Symptom-directed physical examinations will occur at any time during the study if deemed necessary by the investigator.

^k Pregnancy tests will be performed for all female subjects of childbearing potential as described in Section 11.7.2. At assessment time points when telephone contact takes the place of a clinic visit, a urine pregnancy test will be performed with a home kit provided by the study site. Results will be reported to the site by telephone.

^l Blood samples for FSH will be measured as outlined in Section 11.7.2

^m All standard 12-lead ECGs will be performed after the subject has been at rest for at least 5 minutes. ECGs will be collected before dosing (as applicable).

ⁿ Vital signs and pulse oximetry will be collected before dosing and after the subject has been at rest for at least 5 minutes (Section 11.7.3 and Section 11.7.4).

^o Spirometry assessments must be performed before study drug dosing (Section 9.6.1) and should be performed pre-bronchodilator (Section 11.6.1) at approximately the same time each visit.

^p Sweat chloride collection will occur before study drug dosing (Section 11.4). At each time point, 2 samples will be collected, 1 from each arm (left and right).

^q PK samples will be collected predose on Week 4 only as described in Section 11.3.1.

Table 3-1 VX17-659-105: Treatment Period and Safety Follow-up Visit

Event/Assessment ^a	Treatment Period							ETT Visit ^c	Safety Follow-up Visit (28 ± 7 Days After Last Dose) ^d
	Day 1 ^b	Day 15 (± 3 Days)	Weeks 4, 8, 16, 24, 36 (± 5 Days)	Weeks 12, 20, 28, 32, 40, 44, 52, 56, 64, 68, 76, 80, 88, 92 (± 5 Days)	Week 48 (± 5 Days)	Weeks 60, 72, 84 (± 5 Days)	Week 96 (± 5 Days)		
Study drug count	X	X	X		X	X	X	X	
Study drug dosing ^s	Day 1 through evening before Week 96 Visit								
Other events related to outcome ^t	Continuous from signing of the ICF through completion of study participation								
Medications review ^u	Continuous from signing of the ICF through completion of study participation								
Treatments and procedures review ^u	Continuous from signing of the ICF through completion of study participation								
AEs and SAEs ^{u, v}	Continuous from signing of the ICF through completion of study participation								

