11.3 Pharmacokinetics

11.3.1 Blood Sampling

At the Week 4 Visit only, predose blood samples will be collected to determine plasma concentrations of VX-659, TEZ, M1-TEZ, and IVA. These samples may also be used to evaluate metabolites of VX-659 and additional TEZ and IVA metabolites. [REDACTED]

The Week 4 predose samples must be collected within 60 minutes before dosing; all efforts should be made to obtain the PK samples during this specified window. Samples collected outside of the window will be considered protocol deviations.

A record of study drug administration that coincides with the Week 4 PK blood draw will be collected as described in Section 9.6. The collection date and exact time that each PK blood sample is drawn will also be recorded.

Samples from the PK sampling will be kept frozen by Vertex or its designee until all analyses have been completed and then disposed of according to Vertex or designee standard operating procedures.

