11.4 Pharmacodynamics: Sweat Chloride

SwCl samples will be collected with an approved collection device. Each collection will occur before study drug dosing (Section 9.6.1). At each time point, 2 samples will be collected; 1 from each arm (left and right). Sweat samples will be sent to a central laboratory for testing and interpretation of results. Individual SwCl test results will not be disclosed to the study sites. Specific instructions for the collection, handling, processing, and shipping of SwCl samples to the central laboratory will be provided separately.

Subjects (and their parents/caregivers/companions) should not be informed of their study-related SwCl results until Vertex has determined that the study has completed (i.e., CSR finalization), regardless of whether the subject has prematurely discontinued treatment.

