12.4 Clinical Pharmacology Analysis

For the PK analysis, trough concentrations of VX-659, TEZ, and IVA may be summarized using descriptive statistics. Trough concentrations may also be analyzed with prior study PK data using nonlinear mixed-effects modeling, as data allow. A detailed description of the planned PK analysis will be presented in the CPAP.

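### Protocol 9.6.1 has the morning TC dose taken at home before late-afternoon visits, yet spirometry, sweat chloride and the Week 4 PK sample must precede dosing; both cannot be met at such a visit

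*Protocol*

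**What the plan says.** Protocol 9.6.1 sets the timing of dosing on visit days. Under item 4, "the morning dose of TC will be administered at the site after predose assessments have been completed". Item 5 gives binding guidelines for afternoon visits, with two branches. If the clinic dose would come within 6 hours of the scheduled morning dose, the subject withholds it and doses in the clinic. If it would come later than that, "the subject should take the morning dose of TC at home".

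The timing of the assessments is set elsewhere in the protocol:

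- Table 3-1, footnote a: "All assessments will be performed before dosing unless noted otherwise".
- Table 3-1, footnote o (repeated in substance in 11.6.1): "Spirometry assessments must be performed before study drug dosing".
- Section 11.4, sweat chloride: "Each collection will occur before study drug dosing".
- Section 11.3.1, PK: "The Week 4 predose samples must be collected within 60 minutes before dosing". Samples outside that window count as protocol deviations.

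On analysis, Protocol 12.4 says that "trough concentrations of VX-659, TEZ, and IVA may be summarized using descriptive statistics" and leaves the detail to the CPAP. SAP 9.3.2.2 summarises ppFEV1 and sweat chloride by visit. SAP 12.1 selects the record within a visit window by its distance from the target study day.

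**The concern.** Both sets of instructions are firm. A site that follows item 5 at a late-afternoon visit meets a subject who has already taken that day's TC dose, so nothing measured there precedes the morning dose. A site that follows the assessment sections has to depart from item 5.

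Two things are at stake. First, a Week 4 sample taken some hours after dosing is not a trough: all three components are in the morning tablets, and VX-659 and TEZ are given once daily (SAP Table 6-1). Second, the visit series for spirometry and sweat chloride would mix predose and post-dose values with nothing in the SAP to tell them apart.

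**Working it through.** No figure in the plan bears on this point, so the check is a comparison of passages plus timing arithmetic.

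**1. Which assessments conflict**

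| Assessment | Timing required | Allowance for home dosing | Scheduled visits exposed |
|---|---|---|---|
| Spirometry (11.6.1, footnote o) | Before dosing | None | Day 15; Weeks 4, 8, 16, 24, 36, 48, 60, 72, 84 |
| Sweat chloride (11.4, footnote p) | Before dosing | None | Day 15; Weeks 4, 8, 16, 24 |
| PK (11.3.1, footnote q) | 0 to 60 minutes before dosing | None | Week 4 |
| ECG (footnote m) | Before dosing, only where applicable | Yes | Not in conflict |

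Day 1 is not exposed, because the first dose follows that visit's assessments. Week 96 is not exposed, because the final dose is taken the evening before. Vital signs (footnote n, 11.7.3) carry the same unqualified predose wording. Pulse oximetry (11.7.4) has one unqualified sentence and one limited to visits with on-site dosing. Table 3-1 therefore belongs in the reconciliation.

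**2. Timing**

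Let v be the hours from the scheduled morning dose to the time at which the clinic dose would be given. Assume that assessments are made close to that time and that the evening dose comes 12 hours after the morning dose.

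- *Home-dose branch, v > 6.* The home dose is taken before the visit, so assessments fall about v hours after it: 6.5 h at v = 6.5 and 10 h at v = 10. The PK window needs a draw between 1 hour before the dose and the dose itself, which cannot happen here. Even if the home dose is 2 hours late, the limit of the allowance in 9.6.1 item 2, the gap still exceeds 6 − 2 = 4 h.
- *Withhold branch, v ≤ 6.* Assessments fall 24 + v hours after the previous TC dose (26 h at v = 2, 30 h at v = 6) and 12 + v hours after the evening IVA dose (14 h and 18 h). They are predose.

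The conflict is therefore confined to the home-dose branch, where it cannot be avoided.

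**3. What happens to the values**

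- *Spirometry and sweat chloride.* SAP 9.3.2.2 and 12.1 contain no condition, flag or exclusion based on time since dose. A post-dose value enters its visit summary like any other.
- *PK.* An out-of-window Week 4 sample is a deviation under 11.3.1, but no exclusion from analysis follows. It can be identified: 9.6.1 item 3 records the two preceding doses and that morning's dose, and 11.3.1 records the exact draw time. Whether it enters a trough summary depends on the CPAP.

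**4. How many**

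The documents do not give the share s of late-afternoon visits. With the 400 subjects used for planning, 400 × s Week 4 samples are affected: 20 if s = 5% and 80 if s = 20%. Both shares are assumptions, and the result only restates them. The shift per sample depends on kinetics that the documents do not give.

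**The case against.** The best reply is that item 5 is a specific exception inside the section designated to govern timing. Footnote a leaves room for exceptions, footnote s sends the reader to 9.6.1 for dosing relative to assessments on visit days, and 11.4 and 11.6.1 cite 9.6.1 in their predose sentences. Section 11.7.4 shows that visits without on-site dosing were foreseen. This softens the conflict but does not remove it. Item 5 speaks only of dosing and releases no assessment from its timing rule, and 11.3.1 still classes the resulting Week 4 sample as a deviation. Reading the requirement as before the evening IVA dose does not help either, since item 4 ties predose assessments to the morning TC dose.

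It can also be said that nothing obliges a site to book a visit that late, given visit windows of ±3 or ±5 days and the request for spirometry at a similar time each visit. That may make such visits uncommon, but item 5 expressly provides for them.

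A reader might infer that post-dose concentrations will contaminate the trough summary. The documents do not support that. The summary is optional, the samples are identifiable deviations, and the governing CPAP was not available. Nor does the SAP label its spirometry or sweat chloride summaries as predose; they are visit summaries.

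The argument of low consequence stands. SAP Section 3 records the decision to end the study early, SAP 9.3 drops all model-based efficacy analysis, and no test depends on these values. SAP 9.3 also limits the visit summaries to visits with at least 20 subjects per group, so later exposed visits may not be summarised at all.

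**Conclusion.** The contradiction is real. At a visit in the home-dose branch of 9.6.1 item 5, the predose requirements for spirometry, sweat chloride and the Week 4 PK sample cannot be met. That spirometry and sweat chloride values from such visits enter the SAP summaries undistinguished follows from the SAP text. That PK values do so is an open risk, not a stated outcome.

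The impact is low. The affected endpoints are secondary and descriptive, and PK is a single time point. The number of affected visits cannot be derived from the documents. The conclusion assumes only that the home dose is taken before the subject comes to the visit. It takes no view on which dosing or timing rule is right.

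**What to change.** 1. Reconcile 9.6.1 item 5 with 11.3.1, 11.4, 11.6.1 and Table 3-1. Which rule holds is for the sponsor. Because the study is ending early, the analysis steps below matter more than new site instructions.
2. State in the CPAP, if it does not already say so, that the Week 4 trough summary uses only samples confirmed predose from the recorded dose and draw times. Keep the other samples for the nonlinear mixed-effects modelling that Protocol 12.4 allows.
3. Flag post-dose spirometry and sweat chloride values in the listings where dose timing is known. Item 3 of 9.6.1 specifies dose-time recording only around the Week 4 sample, so flags at other visits depend on source records or an added data field and may be incomplete.

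The cost is some protocol wording and one filter on data already collected. The downside is the loss of a few trough values.

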9.6.2 Missed Doses

9.6.2.1 Morning Dose of Study Drug

If a subject misses the morning dose of TC and recalls within 6 hours, the subject should take his/her dose with food. If more than 6 hours but fewer than 12 hours have elapsed after his/her usual dosing time, the subject should take the morning dose of TC but skip the evening dose of IVA. If more than 12 hours have elapsed after his/her usual dosing time, the subject should skip the morning dose of TC and take the evening dose of IVA.

